#### OS

Overall survival is defined as the time from treatment initiation until death from any cause. Median OS time (months) is the timepoint at which the probability of survival equals 50% in the efficacy evaluable population. Patients developing no event will be censored on the last known survival date. Patients providing no follow-up information will be censored on the day of first dosing. Kaplan-Meier method will be used to estimate median OS and the corresponding 95% CI. Kaplan-Meier curves will be constructed to provide a visual presentation of the OS rate change with time.

6-month OS rate is the proportion of efficacy evaluable patients who are alive 6 months after treatment initiation. The OS rate and 95% CI at 6 months will also be summarized.

OS will be displayed for Part A, Part B and Part C.

Waterfall, Spider, Swim-lane and forest Plots

A waterfall plot will be prepared to visually present the best percentage change from baseline in sum of diameters in target lesions for each patient grouped by PD-L1 status, HPV type, and histologic type.

A Spider Plot will be used to visualize changes in sum of diameters in target lesions with best overall response by BICR according to RECIST 1.1. With a Spider Plot, post-baseline measurements are compared to the baseline. Thus, the data plotted is the percent change from baseline over the period of patient evaluation. Each leg of the "spider" represents a unique patient.

Swim-lane Plot for Tumor Response will be presented to show tumor assessment by at each

Document: \\ieedc-vnac01\Biosdata\Genexine\GX-188E\GYA02599\Biostatistics\Documentation\SAP

Author: [name] Version Number: 1.1

Version Date: 05Sep2022

Template No: CS\_TP\_BS016 Revision 6 Reference: CS\_WI\_BS005

PROTOCOL GX-188E-005

Analysis Plan Page 34 of 48

visit. Specifically, the Swim-lane plot will show total time to tumor response, whether the response was complete or partial, when the response started/ended and censoring information of the patient grouped by PD-L1 status, HPV type, and Histologic type.

These plots will be displayed only for Part C.

In Part C, a forest plot will be used to display BICR Assessed BORR according to RECIST v1.1 across subgroups.

#### 15.3. EXPLORATORY EFFICACY ENDPOINTS

Not Applicable.

#### 16. SAFETY OUTCOMES

Safety variables to be analyzed are AEs, laboratory test results (e.g., hematology, coagulation, serum chemistry, thyroid function tests, and urinalysis), vital signs and others.

All outputs for safety outcomes will be based on the safety population. The results will be presented for Part A, Part B Part C and overall except for DLT.

#### **16.1.** ADVERSE EVENTS

An adverse event is any untoward, undesired, or unplanned event in the form of signs, symptoms, disease, or laboratory or physiologic observations occurring in a person given a test article in a clinical study. AEs will be coded using MedDRA 21.1 or higher.

See Appendix 2 for handling of partial dates for AEs. In the case where it is not possible to define an AE as treatment emergent or not, the AE will be classified by the worst case; i.e. treatment emergent.

An overall summary of number and percentage of patients and number of adverse events within each of the categories described in the section below except for DLT, will be provided.

Listings will include both TEAEs and Non-TEAEs. Tables will include TEAEs.

#### 16.1.1. ALL TREATMENT EMERGENT ADVERSE EVENTS

Treatment emergent adverse events are defined as AEs that started or worsened on or after the

 $Document: \underline{\label{locality} Nieedc-vnac01\\Biosdata\\Genexine\\GX-188E\\GYA02599\\Biostatistics\\Documentation\\SAParticles \\Documentation\\SAParticles \\Documentation\\SAParticles \\Documentation\\SAParticles \\Documentation\\SAParticles \\Documentation\\SAParticles \\Documentation\\SAParticles \\Documentation\\SAParticles \\SAParticles \\SAParti$ 

Author: [name] Version Number: 1.1

Version Date: 05Sep2022

Template No: CS\_TP\_BS016 Revision 6 Reference: CS\_WI\_BS005

Effective Date: 02Dec2019

PROTOCOL GX-188E-005

Analysis Plan Page 35 of 48

first dose of study medication. In the case where it is not possible to define an AE as treatment emergent or not, the AE will be classified by the worst case; i.e. treatment emergent.

Incidence of TEAEs will be presented by SOC and PT and also broken down further as shown in the following sections.

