#### 20.0 SAFETY REPORTING AND DOCUMENTATION OF CLINICAL RESULTS

# 20.1 Safety Evaluations

For safety information on GX-188E, refer to the most recent version of the Investigator's Brochure. For safety information on pembrolizumab, please refer to the package inserts.

Routine safety and tolerability will be evaluated from the results of reported signs and symptoms, scheduled physical examinations, vital sign measurements, and clinical laboratory test results.

More frequent safety evaluations than required by this protocol may be performed if clinically indicated and at the discretion of the Investigator. All adverse events (AEs) will be recorded from the time the patient receives the first dose of the investigational treatment regimen to 28 days after the last dose.

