# 20.2 Adverse Events (AE)

The Investigator will evaluate all adverse events (AEs) according to the NCI Common Terminology Criteria for Adverse Events Version 4.0 or the most recent version. An **adverse event** (AE) is any untoward, undesired, or unplanned event in the form of signs, symptoms, disease, or laboratory or physiologic observations occurring in a person given a test article in a clinical study. The event does not need to be causally related to the investigational treatment. An AE includes, but is not limited to, the following:

- Any clinically significant worsening of a preexisting condition
- An AE occurring from overdose (i.e., a dose higher than that indicated in the protocol) of a test article, whether accidental or intentional
- An AE occurring from abuse (e.g., use for nonclinical reasons) of a test article
- An AE that has been associated with the discontinuation of the use of a test article

Any treatment-emergent abnormal laboratory result which is clinically significant, i.e., meeting one or more of the following conditions, should be recorded as a single diagnosis on the adverse event page in the CRF:

- Accompanied by clinical symptoms
- Leading to a change in study medication (e.g., dose modification, interruption, or permanent discontinuation)

• Requiring a change in concomitant therapy (e.g., addition of, interruption of, discontinuation of, or any other change in a concomitant medication, therapy or treatment)

Clear progression of the patient's primary malignancy should not be reported as an AE, unless it results in hospitalization or death. Findings that are clearly consistent with the expected progression of the underlying cancer should not be reported as an adverse event, and hospitalizations due to the progression of cancer do not necessarily qualify for an AE. If there is any uncertainty about a finding being due solely to progression of primary malignancy, the finding should be reported as an AE as appropriate.

AEs should be considered treatment-related, unless they fulfill the following criteria:

- Evidence exists that the AE has an etiology other than the investigational product (e.g., preexisting medical condition, underlying disease, intercurrent illness, or concomitant medication), and/or
- The AE has no plausible temporal relationship to administration of the investigational product (e.g., a new cancer diagnosed 2 days after first dose of study drug).

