### GX-188E/Pembrolizumab [Protocol Number: GX-188E-005] Amended (V4.0)\_29Aug2022

- 1. Medical history includes any significant comorbid conditions requiring active treatment as well as surgeries and therapies related to the treatment of malignancies, including cervical cancer. Cervical cancer history includes review of prior treatments and documentation of HPV-16 or -18 positivity. Medical records and/or local laboratory results will be considered adequate documentation HPV-16 or -18 positivity
- 2. Screening and End of Study require a complete physical exam. For all other study, physical exams should be symptom-directed and clinically significant findings reported as adverse events.
- 3. Vitals to include heart rate, respiratory rate, temperature, blood pressure (systolic and diastolic) weight, and height. Height only required at screening
- 4. Determine whether the patient has low risk, mid risk or high risk disease based upon Moore criteria (See Appendix 3).
- 5. Adverse event monitoring begins once a patient receives the first dose of study treatment and continues until 28 days after the last administration of study treatment, or until the initiation of a new anti-cancer therapy, whichever occurs first. For Serious Adverse Events (SAEs), follow up will continue for 90 days.
- 6. Concomitant medication is defined as any prescription or over-the-counter preparation, including vitamins and supplements. All concomitant medications from 28 days before Day 1 through the end of the subject's study participation must be recorded. (During the follow-up period after the end of the clinical trial, only the data about the antineoplastic therapy (surgical therapy, chemotherapy, radiation therapy, etc.) treated after the end of the subject's study participation is recorded.)
- 7. CBC w/differential to include: Hemoglobin, Platelets, Red Blood Cells, White Blood Cells, Basophils (%)), Eosinophils (%)), Lymphocytes (%), Neutrophils (Abs) and Hematocrit.

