## **ALGORITHM FOR TREATMENT EMERGENCE OF ADVERSE EVENTS:**

START DATE	STOP DATE	ACTION
Known	Known	If start date < study med start date, then not TEAE  If start date >= study med start date, then TEAE
	Partial	If start date < study med start date, then not TEAE  If start date >= study med start date, then TEAE
	Missing	If start date < study med start date, then not TEAE  If start date >= study med start date, then TEAE
Partial, but known components show that it cannot be on or after study med start date	Known	Not TEAE
	Partial	Not TEAE
	Missing	Not TEAE
Partial, could be on or after study med start date	Known	If stop date < study med start date, then not TEAE  If stop date >= study med start date, then TEAE

Document: \\ieedc-vnac01\Biosdata\Genexine\GX-188E\GYA02599\Biostatistics\Documentation\SAP

Author: [name] Version Number: 1.1

Version Date: 05Sep2022

Template No: CS\_TP\_BS016 Revision 6 Reference: CS\_WI\_BS005

Effective Date: 02Dec2019

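### The SAP's treatment-emergence algorithm leaves out the worsening half of its own TEAE definition, and the protocol gives three different end points for AE collection

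*SAP*

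**What the plan says.** **Treatment emergence.** SAP 16.1.1 sets the definition: "Treatment emergent adverse events are defined as AEs that started or worsened on or after the" first dose of study medication. It gives no end date. It adds a worst-case default, but only for events whose emergence cannot be determined.

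SAP Appendix 2 gives the operating rule under the sub-heading "ALGORITHM FOR TREATMENT EMERGENCE OF ADVERSE EVENTS". For a known start date, all three stop-date rows contain "If start date < study med start date, then not TEAE". For a start date described as "Partial, but known components show that it cannot be on or after study med start date", all three rows return not TEAE.

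SAP 16.1 fixes the consequence: "Listings will include both TEAEs and Non-TEAEs. Tables will include TEAEs".

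**AE collection.** The protocol states the end of AE collection in three ways:
- Section 20.1 records AEs from "first dose of the investigational treatment regimen to 28 days after the last dose".
- The Appendix 1 Schedule of Events footnotes (footnote 5 up to Week 10, footnote 3 afterwards) end monitoring at "28 days after the last administration of study treatment, or until the initiation of a new anti-cancer therapy, whichever occurs first".
- Section 20.6.1, the section on collection periods, runs AEs to 30 days after treatment stops, with no cut-off for new therapy.

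**The concern.** A programmer applies an algorithm as it is written. If the algorithm omits one half of the definition, the tables will follow the algorithm and the SAP text will describe something else. The case at risk is an AE whose record carries an onset before first dose and whose grade rises on treatment. Under 16.1.1 it belongs in the TEAE tables. Under Appendix 2 it does not, so it would also be missing from the breakdowns by severity and relationship that are built on those tables.

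The second issue concerns data collection. Sites that follow different sections of the same protocol could stop recording non-serious AEs on different days, so the post-treatment part of the safety tables might not be collected uniformly.

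**Working it through.** No sample size, power or alpha is involved, and the plan gives no figure to reproduce. The check sets the rules side by side.

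**1. Appendix 2 against SAP 16.1.1**

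| Start date | Rows (stop known, partial, missing) | Result | Post-dose worsening |
|---|---|---|---|
| Known | 3 | Before first dose: not TEAE. On or after: TEAE | Missed in the pre-dose branch |
| Partial, must be pre-dose | 3 | Not TEAE | Missed |
| Partial, could be on or after first dose | 3 | TEAE unless the stop date is before first dose | Captured in effect |
| Missing | 3 | TEAE unless the stop date is before first dose | Captured in effect |

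- Rows: 4 start-date classes × 3 stop-date classes = 12.
- Rows that can return not TEAE on a definite pre-dose start alone: 3 + 3 = 6. The 3 known-start rows hold both outcomes, so only the 3 partial-start rows are purely pre-dose.
- Rows that test for worsening or a grade change: 0 of 12.

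Example: an AE record with a known start before first dose reaches Grade 3 after dosing. SAP 16.1.1 makes it a TEAE because it worsened. Appendix 2 makes it not a TEAE because of its start date. The worst-case default does not rescue it, because the algorithm returns a definite answer. Had the start date been missing, the same event, still open after first dose, would have counted.

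**2. AE collection end dates**

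Let day 0 be the last dose, taken here as the same day as cessation of treatment (an assumption). Let new anticancer therapy start on day d.

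| Source | Rule | No new therapy | d = 10 (illustrative) |
|---|---|---|---|
| Protocol 20.1 | 28 | 28 | 28 |
| Appendix 1 footnotes | min(28, d) | 28 | 10 |
| Protocol 20.6.1 | 30 | 30 | 30 |

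- No new therapy: 30 − 28 = 2 days between the earliest and latest end dates.
- New therapy on day d, assumed range 1 to 28: spread = 30 − d. At d = 28 this is 2 days, at d = 10 it is 20, and at d = 1 it is 29.

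These spreads are between written rules, not between visits. Protocol 16.12 places the End of Study visit within 28 days of stopping treatment and before any new anticancer therapy. Long-term follow-up (16.13) then asks only about survival and subsequent treatment. The last scheduled AE check therefore falls no later than any of the three cut-offs. What differs is how long a site must keep recording AEs that come to its attention otherwise.

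**The case against.** On the first part, Appendix 2 is titled as a set of partial-date conventions, and SAP 7.3 and 16.1 send the reader there for partial dates only. The definition itself sits in 16.1.1 and includes worsening. This carries some weight, but the sub-heading announces a treatment-emergence algorithm and the first row is a known start with a known stop, so the appendix does classify complete dates.

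The stronger point is practical reach. AE recording begins at first dose (protocol 20.1), and the AE definition in 20.2 includes "Any clinically significant worsening of a preexisting condition". A worsening entered as its own AE has a post-dose onset and passes the algorithm. That stands, and it is why few events are expected. It does not close the gap. Neither document says that a worsening must be a new record with its own onset date, and the SAP expects non-TEAE records to exist because it lists them.

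On the second part, a reader might infer that the collection windows for events of clinical interest (ECIs) and SAEs conflict in the same way. The documents do not support that:
- **ECIs.** Section 20.6.1 sets collection to 30 days. The window in 20.8, which also stops at new therapy, limits which ECIs must reach the sponsor within 24 hours. The two can coexist.
- **SAEs.** The footnotes speak of follow-up for 90 days, the same base period as 20.6.1. They leave out its shortening to 30 days when new therapy starts. Drug-related SAEs that come to an investigator's attention are reportable at any time under 20.6.1.

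Nor do late SAEs risk dropping out of the TEAE tables, because the definition in 16.1.1 has no end date.

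**Conclusion.** Both parts hold on the text, and both are minor. Appendix 2 does not implement the TEAE definition in SAP 16.1.1: the pre-dose branch of 3 rows and the whole of 3 others exclude an event without asking whether it worsened. The number of events cannot be derived from the documents. It is probably small and depends on CRF design and completion rules that are not shown. The row count describes the gap in the rule, not its effect on results.

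The AE end dates conflict both in the day count (28 against 30) and in whether new therapy stops collection. The nominal spread is 2 days without new therapy and up to 29 days under the assumed range for d. Its practical effect is limited by the timing of the End of Study visit.

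Only descriptive safety tables are touched. ORR24 rests on tumor assessments, and DLTs are identified by their own CRF question, so neither is affected.

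**What to change.** 1. **SAP Appendix 2.** In the pre-dose branch of the 3 known-start rows and in the 3 partial-start rows that must be pre-dose, add: if the CTCAE grade increased on or after the study medication start date, classify as TEAE. Where the CRF has no dated grade change, require the worsening to be entered as a new AE record with its own onset date.
2. **Protocol.** Make 20.6.1 the single AE rule (30 days), and align 20.1 and both Schedule of Events footnotes to it.
3. **Tidy-ups only.** Add the new-therapy exception from 20.6.1 to the SAE sentence in both footnotes, and state that the window in 20.8 governs 24-hour ECI reporting.

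The cost is SAP and protocol wording and perhaps one CRF completion instruction. Adopting 20.6.1 has a small downside: AE collection continues to day 30 even after new anticancer therapy starts, and a day-30 phone check may be needed because the End of Study visit falls within 28 days.

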#### 16.1.1.1. Severity

The severity of all TEAEs shall be graded according to 5 grades (Grade 1 to Grade 5) in accordance with the national cancer institute common terminology criteria for adverse event (NCI CTCAE) V4.0 or the most recent version.

If a patient reports a TEAE more than once within that SOC/ PT, the AE with the worst-case severity will be used in the corresponding severity summaries.

#### 16.1.1.2. Relationship

Relationship to study medications, as indicated by the Investigator, is classed as Probably related, "Possibly related," "Unlikely related," and "Unrelated," (decreasing in severity of relationship).

If a patient reports the same AE more than once within that SOC/ PT, the AE with the worst-case relationship to study medications will be used in the corresponding relationship summaries.

#### 16.1.2. TREATMENT RELATED ADVERSE EVENTS (TRAE)

TRAE is defined as an AE with relationship to study medications as "Probably related" or "Possibly related" to GX-188E and/or Pembrolizumab. TRAEs with a missing relationship to study medication will be regarded as "Probably related" to study medication.

Summary tables for all TRAEs will be tabulated together. TRAEs with Relationship to GX-188E and TRAEs with Relationship to Pembrolizumab will be also summarized separately.

#### 16.1.3. TEAES LEADING TO DISCONTINUATION OR INTERRUPTION OF STUDY MEDICATION

TEAEs leading to drug interruption of GX-188E will be identified by using the "Action Taken with GX-188E" with answer "Drug Interrupted" from the AE page of the CRF. TEAEs leading to drug interruption of pembrolizumab will be identified by using the "Action Taken with pembrolizumab" with answer "Drug Interrupted" from the AE page of the CRF.

TEAEs leading to permanent discontinuation of GX-188E will be identified by using the "Action Taken with GX-188E" with answer "Drug withdrawn" from the AE page of the CRF. TEAEs leading to permanent discontinuation of pembrolizumab will be identified by using the "Action

Document: \\ieedc-vnac01\Biosdata\Genexine\GX-188E\GYA02599\Biostatistics\Documentation\SAP

Author: [name] Version Number: 1.1

Version Date: 05Sep2022

Template No: CS\_TP\_BS016 Revision 6 Reference: CS\_WI\_BS005

PROTOCOL GX-188E-005

Analysis Plan Page 36 of 48

Taken with pembrolizumab" with answer "Drug withdrawn" from the AE page of the CRF.

For TEAEs leading to discontinuation or interruption of study medication, summaries of incidence rates (frequencies and percentages) by SOC and PT will be prepared.

#### 16.1.4. AEs Leading to Study Discontinuation

TEAEs leading to study discontinuation will be identified by using the "Did this event lead to withdrawal from the study?" with answer "Yes" from the AE page of the CRF.

For TEAEs leading to study discontinuation, summaries of the number and percentage of patients by SOC and PT will be prepared. For TRAEs leading to study discontinuation will be summarized in the same way.

#### 16.1.5. AES LEADING TO DEATH

TEAEs leading to death are those events which are recorded as "Fatal" on the Adverse Events page of the CRF.

A summary of TEAEs and TRAEs leading to death by SOC and PT will be prepared.

#### 16.1.6. SERIOUS ADVERSE EVENTS

All AEs will be evaluated for seriousness. A serious adverse event (SAE) is an AE that meets at least one of the following criteria:

- Results in death (NOTE: death is an outcome, not an event)
- Is life-threatening
- Requires inpatient hospitalization or prolongation of an existing hospitalization
- Results in a persistent or significant disability or incapacity
- Results in a congenital anomaly or birth defect
- Additionally, important medical events that may not result in death, be life-threatening, or require hospitalization may be considered SAEs when, based on appropriate medical judgment, they may jeopardize the patient and may require medical or surgical intervention to prevent one of the outcomes listed in this definition. Examples of such events include allergic bronchospasm requiring intensive treatment in an emergency room or at home, blood dyscrasias or convulsions that do not result in hospitalization, or development of drug dependency or drug abuse.

SAEs will be identified as those events recorded as "Serious" on the Adverse Events page of

Author: [name] Version Number: 1.1

Version Date: 05Sep2022

Template No: CS\_TP\_BS016 Revision 6 Reference: CS\_WI\_BS005

Analysis Plan Page 37 of 48

the CRF.

Summaries of all SAEs and SAEs Related to study medications by SOC, PT and Maximum CTCAE Grade will be prepared.

#### 16.1.7. DOSE LIMITING TOXICITY (DLT)

A DLT is defined as any AE that is not clearly due to progression of the patient's primary malignancy, occurs within the DLT window of observation period, and that meets at least one of the criteria below:

Non-Hematologic Dose Limiting Toxicities:

Any CTCAE (v4 or the most recent version) AE of ≥ Grade 3 treatment-related non-hematological toxicity except for the following:

o nausea, vomiting, or diarrhea lasting ≤ 72 hr

o Grade 3 fatigue lasting ≤ 7 days

o hypersensitivity reactions lasting ≤ 72 hrs

o Grade 3 hyperglycemia lasting ≤ 72 hr with standard anti-diabetic therapy

o Grade 3 increases in liver transaminases in patients with liver metastases. (Note: Grade 4 increases in LFTs in any patient will be considered a DLT)

o clinical laboratory abnormalities that are reversible to ≤ Grade 1 or baseline status within 72 hr with outpatient care and/or monitoring, or that are considered not clinically significant by the Principal Investigator

Hematologic Dose Limiting Toxicities:

o Grade 4 neutropenia (ANC < 0.5 x10^9/L)

o Grade 3 febrile neutropenia (ANC < 1.0 x 10^9/L with temperature ≥ 38.3°C)

o Grade 4 thrombocytopenia (platelet count <  $25.0 \times 10^9$ /L) lasting > 4 days or that requires platelet transfusion

o Grade  $\geq$  3 thrombocytopenia (platelet count < 50.0 x 10 $^{9}$ /L) associated with Grade  $\geq$  3 bleeding

o Any hematologic toxicity resulting in death (i.e. Grade 5)

In addition, any other AE that is felt to be treatment-limiting in the medical opinions of the Principal Investigator and the Sponsor's Medical Monitor may be considered a DLT. These include, but are not limited to the following:

Author: [name] Version Number: 1.1

Version Date: 05Sep2022

Template No: CS\_TP\_BS016 Revision 6 Reference: CS\_WI\_BS005

Effective Date: 02Dec2019

Analysis Plan Page 38 of 48

o Any toxicity leading to more than one missed dose of either GX-188E or pembrolizumab during the DLT-evaluation period

o Any toxicity leading to > 2 weeks delay in initiation of the 2nd cycle of pembrolizumab.

The DLT window of observation will be during Cycle 1 of pembrolizumab (ie., the first 3 weeks of treatment prior to week 4 Day 1 visit).

A DLT will be identified on "Adverse Events" form of CRF with the response of "Yes" to the question "Is this AE considered as a DLT (Dose-Limiting Toxicities)?".

Summaries of DLTs by DLT Category, SOC, PT and Maximum CTC Grade will be prepared for DLT evaluable population in Part A.

